5.2.3 Exclusion Criteria

For exclusion criteria, subjects should not enter the study if any of the following exclusion criteria are filled:

- 1. Diagnosed with chronic pain syndrome
- 2. Body Mass Index (BMI) ≥ 40
- 3. Current tobacco user at time of surgery
- 4. Uncontrolled sleep apnea
- 5. Bilateral TKA
- 6. Current or recent history (in past year) of substance abuse disorder

PI Name: [name] Research Protocol: July 25, 2019 Version 1.2 (03/17/20)

- 7. Uncontrolled diabetes (HbA1c \geq 7.0) 7.8 at time of surgery
- 8. History of Pulmonary Embolism (PE) or Deep Vein Thrombosis (DVT)
- 9. Currently being treated with blood thinners at time of surgery
- 10. Diagnosis of Rheumatoid Arthritis (RA)
- 11. Has Methicillin-resistant Staphylococcus aureus (MRSA)
- 12. Currently pregnant/breastfeeding or planning to in the next 3 months
- 13. Comorbidities including neurological, psychosocial, sensory, or other disorders that may impact pain perception
- 14. Diagnosis of epilepsy, dementia, migraines, or other neurological disorders that may prevent VR usage, and/or other medical conditions predisposed to nausea and dizziness
- 15. Hypersensitivity to flashing lights or motion
- 16. Claustrophobia
- 17. Lack of stereoscopic vision
- 18. Severe hearing impairment
- 19. Injury to eyes, face, or neck that prevents comfortable VR usage

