5.4.2 Approximate Duration of Study

This study will be completed in approximately two years. The end of the study is the last visit of the last subject or end of collection of data from the patient's electronic medical record (EMR).

PI Name: [name] Research Protocol: July 25, 2019 Version 1.2 (03/17/20)

5.5 **PROCEDURES**

Standard of Care: Both the SOC+RelieVRx group and the SOC group will be enrolled in the Geisinger ProvenRecovery Program[©], which includes a "My Rapid Recovery Kit" containing care instructions for mobility and nutrition, an antiseptic body wash to lessen the chances of infection, a spirometer to measure lung capacity, and immunonutrition drinks to avoid malnutrition and dehydration. Surgery through ProvenRecovery[©] is opioid avoiding and in many cases opioid free. During surgery, a patient's pain is controlled by targeting only the surgical area. Known as multi-modality pain management, this technique allows for effective pain control of just one area and eliminates additional pain sources. A combination of non-opioid medications is used, depending on the surgery, such as a local anesthesia, ibuprofen, acetaminophen, gabapentin, ketamine, and lidocaine.

Intervention: For all participants who are randomly assigned to the SOC+RelieVRx group, the RelieVRx headset will be provided by a study team member during the preoperative period, along with instructional materials. While in the hospital, use of the VR headset will be offered either in addition or as an alternative to SOC pain medication. The headset will be provided preoperatively, but patients will not be instructed to use the device until after their surgery. Patients will be instructed to use the device on the day of surgery after they are discharged from the Post Anesthesia Care Unit (PACU) to the inpatient unit, or at least 4 hours post-surgery. The device will then go with the patient upon discharge for use through the entire treatment period (i.e. 14 days). Participants will use the RelieVRx headset for 14 days postoperatively a maximum of 3 times per 24-hour period (morning, noon, and evening) for not more than 30 minutes consecutively. The patients will be instructed not to use the device while ambulating.

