5.6 STUDY ENDPOINTS AND STATISTICAL PLAN

This study will evaluate two primary endpoints – effectiveness of a single use of RelieVRx in the reduction of acute postoperative pain by 20%; and overall effectiveness of RelieVRx as an opioid-sparing intervention, where opioid and non-opioid consumption is reduced by at least 20% over a 90-day postoperative period in the SOC+VR group compared to the SOC group.

Acute effectiveness will be evaluated using NPRS data collected before and after each use of RelieVRx (up to 3 times per day) over the 14-day postoperative period. NPRS is measured on a scale of 0-10, with 0 being the least amount of pain and 10 being the most. Because pain levels will vary by time of day administered and are expected to peak in the first 24-72 hours postoperatively and drop afterward, acute effectiveness will be evaluated at all stages of recovery. The expected 20% reduction after single use will be scaled relative to the pre-use pain score [e.g. users reporting a pre-VR pain level of 8 would need to report post-VR pain levels of 6.4 (8 * 80%) on average; users reporting pre-VR pain of 5 would need to report pain levels of 4 post-VR, etc.]. Each SOC+VR patient will use VR up to 44 times over the 14-day recovery period, requiring linear mixed model analysis to assess acute changes in pain scores while accounting for stage of recovery and other covariates, such as age, preoperative health status and opioid use, and postoperative complications. For interim and final endpoint analyses, pain %change scores will be calculated for each use and averaged for each patient across the 72-hour acute postoperative period, the following week, after 10 days, and overall. These averages will be evaluated using one-sample unpaired *t*-tests (or the nonparametric one-sample Wilcoxon signed-rank test, as needed for non-normal data).

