Additional outcome data will be compared between groups in preliminary analyses using chisquared tests (for categorical variables), unpaired Student's t-tests (for single-measure normal continuous data), or nonparametric equivalent (for non-normal data), as appropriate. For measures collected at multiple time points, %AUC values will be calculated per patient and compared using aforementioned tests. In final analyses, outcomes will be compared using linear mixed models, allowing for data missing at random and evaluation of covariates.

When approximately 25% of the total required sample has been collected, patient data will be summarized to verify adequate study power, and interim analyses will be conducted. In order to preserve a Type I error rate of 5% (i.e., $\alpha = 0.05$) for final analyses, interim analyses will be conducted with *p*-value threshold of 0.001, as suggested using the Hybittle-Peto method, meaning that only effects where d > 2.0 will be significant. Additional patients may be recruited as needed to ensure sufficient study power, and fewer patients may be recruited if interim analyses demonstrate highly significant effects. All statistical analyses will be performed with SAS (SAS 9.4, SAS Institute, Cary, NC), Stata (SE 14.2, StataCorp, LLC, College Station, TX), or R (R 3.5.2, The R Foundation, Vienna, Austria) statistical software, with p-values of <0.05 considered statistically significant.

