5.6.1 Sample Size Considerations

This study has been designed with consideration for power requirements of both primary and secondary endpoint evaluations, as well as requirements for a noninferiority trial evaluating the overall effectiveness of RelieVRx as an opioid-sparing product.

Primary Endpoints

Preliminary data collected at Geisinger Medical Center (Danville, PA) between March 2017 and December 2018 from 1,052 patients who underwent total joint arthroplasty showed an average postoperative pain score of 8.50 following the procedure, and 6.16 on day 2 (SD = 2.0; change d = 1.2, or a 28% pain reduction) under SOC.

To assess the acute effectiveness endpoint of 20% average reduction in pain scores, each onesample *t*-test only requires data from 13 patients to demonstrate a significant difference from zero, assuming 20% attrition, a Type I error rate of 5% and a Type II error rate of 20% (i.e., 80%

PI Name: [name] Research Protocol: July 25, 2019 Version 1.2 (03/17/20) power). In order to observe significance of a lower threshold (e.g., a 10% reduction in pain level on average), data from **43 patients using VR** will be required, assuming 20% attrition, a Type I error of rate 5% and 80% power.

To assess the overall effectiveness for reducing opioid usage by at least 20%, this study assumes an average MME per day of 12.5mg (SD = 3) across all users, although continuous opioid users may report averages higher than 50mg/day. Observing a 20% relative reduction in opioid usage in the SOC+VR group compared to SOC (2.5mg) will require **64 patients total (32 per group)**, assuming 25% attrition, a Type I error rate of 5% and 80% power. If interim data analysis reveals unexpectedly high variability in opioid consumption, a revised power calculation based on new data may increase data collection requirements to address this question.

Secondary Endpoint

Using aforementioned preliminary data, two patients groups were created with simulated VAS-%AUC data (with day 14 VAS means of 6.16 and 4.93, SD = 2.0; or, a 20% greater reduction at day 14) corresponding to a 7% difference in VAS-%AUC (0.86 versus 0.79; SD = 0.1; difference d = 0.7). Assuming 25% attrition, the study will require **92 patients total** (**46 per group**). Data from at least 68 patients is needed to observe a statistically significant VAS-%AUC difference between SOC and SOC+VR of 7% in an unpaired *t*-test, with a Type I error rate of 5% and 80% power.

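### The additional opioid mixed model adjusts for analgesic use and dose changes that arise after randomisation; separately, the SD of 3 behind the opioid sample size is an unsourced assumption shown without a range

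*Combined protocol and SAP*

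**What the plan says.** **Analysis.** Section 5.6 names two primary endpoints. The second is a reduction of at least 20% over 90 days, VR arm against control, and section 5.6 words it to cover opioid and non-opioid consumption together. Specific Aim 3 (section 4.3) speaks of opioids only. Average MME per day is compared by unpaired t-test or Wilcoxon rank-sum test. A further mixed model of use over time then takes in covariates. The examples given are other analgesics used after surgery, opioid use before surgery, and changes of dose.

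**Sample size.** Section 5.6.1 assumes "an average MME per day of 12.5mg (SD = 3) across all users, although continuous opioid users may report averages higher than 50mg/day". For a 2.5 mg difference it requires 64 patients (32 per group), with 25% attrition, 5% type I error and 80% power. Section 5.2.1 plans about 100 patients, 50 per group.

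**Safeguards.** Section 5.6.1 adds: "If interim data analysis reveals unexpectedly high variability in opioid consumption, a revised power calculation based on new data may increase data collection requirements". Section 5.6 says "When approximately 25% of the total required sample has been collected, patient data will be summarized to verify adequate study power" and "Additional patients may be recruited as needed to ensure sufficient study power".

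**The concern.** Randomisation makes the arms comparable at baseline. Conditioning on something that happens later, and that treatment can alter, gives up that protection. If VR relieves pain, it may change how much non-opioid analgesic a patient takes and whether doses are raised or tapered. A model that holds these fixed no longer estimates the overall effect of VR on opioid use. This is the only between-group primary endpoint and it carries the opioid-sparing claim. An adjusted estimate that disagrees with the unadjusted test would be hard to explain.

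The sample-size input raises a separate question. SD 3 has no stated source: the 1,052-patient local data in section 5.6.1 are reported as pain scores only. It also fits poorly with users above 50 mg/day mentioned in the same sentence. A reader sees one power figure and cannot tell how far it depends on that input.

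**Working it through.** **1. The covariates, one by one**

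- *Opioid use before surgery.* A baseline variable, collected pre-surgery in the section 5.5.1 table. Suitable for adjustment.
- *Other analgesics after surgery.* Follows randomisation. Under the section 5.6 wording it is part of the endpoint. Under Aim 3 it is not, but VR can still affect it. In the section 5.5.1 table, analgesic use is marked through the daily 14-day period and not at the 14, 30, 60 and 90-day column, whereas opioid use is marked there. As the table reads, a 90-day model would lack this covariate for most of the period.
- *Dosage changes.* Not defined. If it means opioid dose changes after surgery, it is built into MME per day, and the outcome is partly adjusted for itself.

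In a linear model, let T be the overall VR effect on MME per day, a the VR effect on the later covariate, and b that covariate's slope on opioid use within arms. The adjusted difference is T − a·b. Take T = −2.5 mg/day, the plan's own effect. The products below are assumptions for illustration:

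| a·b (mg/day) | adjusted difference (mg/day) |
|---|---|
| 0 | −2.5 |
| −0.5 | −2.5 + 0.5 = −2.0 |
| −1.25 | −2.5 + 1.25 = −1.25 |
| +0.5 | −2.5 − 0.5 = −3.0 |

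The documents give neither a nor b, so neither the size nor the direction is known.

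**2. The plan's sample size**

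Two-sided t-test (noncentral t), 5%, 80% power, d = 2.5/3 = 0.833: 23.6, rounded up to 24 per group. 24/0.75 = 32, total 64. This reproduces exactly. Sidedness is not stated; two-sided is inferred because it gives the plan's figure.

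**3. SD 3 against users above 50 mg/day**

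50 is (50 − 12.5)/3 = 12.5 SDs above the mean. The one-sided Chebyshev (Cantelli) bound is 1/(1 + 12.5²) = 1/157.25 = 0.64%. Whatever the distribution, no more than that share can average 50 or more. If 1% of patients sat at 50 with the overall mean held at 12.5, the rest would average (12.5 − 0.5)/0.99 = 12.12. The between-subgroup SD would be √(0.01 × 0.99) × 37.88 = 3.77, and the overall SD √(3.77² + 0.99 × 9) = 4.8 if the rest have SD 3.

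**4. Power for 2.5 mg/day at 100 enrolled, t-test, normal data**

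100 × 0.75 = 75 evaluable; 37 per group is used.

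| SD | 37 per group (25% attrition) | 50 per group (none) |
|---|---|---|
| 3 | 94% | 98.5% |
| 3.8 | 80% | 90% |
| 5 | 56% | 70% |

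At 37 per group, 80% power needs d = 0.660, so the limiting SD is 2.5/0.660 = 3.79. With 50 per group the limit is about 4.4.

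**5. Spread caused by a few heavy users**

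Simulation at 37 per group: heavy users normal with mean 50 and SD 5, others SD 3, overall mean 12.5, VR arm multiplied by 0.8. The shares are assumptions.

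| share | t-test | rank-sum |
|---|---|---|
| 1% | about 74% | about 95% |
| 2% | about 56% | about 92% |
| 5% | about 27% | about 82% |

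**6. An SD trigger at the interim**

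The 3.8 in step 4 is a within-arm SD. If 25 patients are summarised without separating arms, the SD also contains the treatment effect. At a true SD of 3 with the planned effect it is about √(9 + 2.5²/4) = 3.25. In simulated normal data the lumped SD exceeds 3.8 in 11% of trials and the within-arm SD in 3%.

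**The case against.** Four points on the other side have force.

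- *The mixed model is additional.* True. A reader might infer that the primary opioid result is biased. The documents do not support that: the main comparison is an unadjusted t-test or rank-sum test. The objection limits the damage but does not justify the covariates.
- *The plan anticipates high variability.* True. It enrols 100 against 64 needed, allows a revised calculation and extra recruitment, and lists a rank-sum test. What remains missing is the source of the SD and a power range.
- *Some likely heavy users are excluded.* Section 5.2.3 removes "Diagnosed with chronic pain syndrome" and "Current or recent history (in past year) of substance abuse disorder". Preoperative opioid use as such is not excluded, and section 5.6 treats it as a covariate, so some such patients are expected.
- *Attrition may be below 25% here.* Section 5.5 draws opioid data partly from the medical record and the prescription database, which need no patient diary. This stands, and is why step 4 shows both columns.

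Three stronger readings are tempting. The first is that the trial has only 56% power. SD 5 is an illustration, not a figure in the plan, and the one source of extra spread the plan mentions is heavy users, where rank-sum holds up. The second is that many patients will record zero use, because section 5.5 says surgery in the programme "is opioid avoiding and in many cases opioid free". That describes surgery and is weak evidence about 90 days. The third is that "as needed for non-normal data" governs the choice of opioid test. It belongs to the one-sample pain analysis; for the opioid comparison section 5.6 lists both tests without a condition.

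**Conclusion.** The main point holds. As written, the additional between-group opioid model conditions on other postoperative analgesics and dosage changes, so its group difference is not the overall effect of VR on opioid use. The size and direction of the distortion cannot be found from the documents. The conclusion for dosage changes assumes that the term means changes after surgery.

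The secondary point is one of reporting. The 64 patients and 80% power are right for SD 3. At 100 enrolled with the plan's attrition, there is room up to an SD of about 3.8 for the t-test with normal data. Beyond that, the loss depends on the cause: large if the spread is general, small for rank-sum if a few heavy users produce it. The true SD is unknown, so a range is the honest statement; a claim that the trial is underpowered is not supported.

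**What to change.** 1. **Section 5.6, opioid mixed model.** Delete other postoperative analgesics and dosage changes from the between-group model. Adjust for baseline variables only, including preoperative opioid use, which is already collected. Report any analysis that brings in postoperative analgesics as descriptive.
2. **Section 5.6.1.** Label SD 3 an assumption, or give its source if there is one. Replace the single power figure with the range in steps 4 and 5, for both listed tests, with the attrition stated.
3. **Interim re-estimation, if kept.** Base it on the SD without comparing arms. Calibrate any trigger to that lumped SD and to the test chosen. Do not use 3.8, which is a within-arm limit for a t-test with normal data.

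The cost is wording and a little calculation. No data are added and no extra recruitment is forced. The stated power will look less favourable. Choosing a single lead test is a trade-off: rank-sum does better with a few heavy users and slightly worse with normal data, and it does not itself estimate a 20% reduction in the mean.

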5.2 STUDY POPULATION

5.2.1 Approximate Number of Subjects

Approximately 100 Geisinger subjects who have TKA surgery at Geisinger will participate in this study (50 will be in the SOC group and 50 will be in the SOC+RelieVRx group).

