Overall effectiveness will be evaluated by tracking daily opioid usage 90 days postoperatively in both SOC and SOC+VR groups. Average MMEs (Morphine Milligram Equivalents) per day will be compared using unpaired Student's *t*-test (or the nonparametric Wilcoxon rank-sum test) in interim and final endpoint analyses. In addition, changes in usage over time will be evaluated using linear mixed models (or nonlinear models, given data shape), accounting for variations in recovery time across patients and other covariates, such as other analgesic medications used postoperatively, preoperative opioid use, and dosage changes. A sub-analysis will compare usage in the 14-day acute postoperative recovery period.

The secondary endpoint of this study is a comparison of the cumulative experience of pain over the 14-day acute postoperative period between SOC and SOC+VR groups. In order to quantify pain that fluctuates over time, NPRS pain scores will be plotted for each patient over the acute postoperative period, using straight-line interpolation between measurements. This approach will allow for incorporation of all data collected (even if some patients participate more than others), and will avoid overemphasis on a single outcome measure (e.g. pain on day 14). Percent-areaunder-the-curve (VAS-%AUC) measurement will be calculated for each patient by adding the

PI Name: [name] Research Protocol: July 25, 2019 Version 1.2 (03/17/20)

areas of consecutive trapezoids defined by time on the x-axis and pain level measurements on the y-axis (e.g. 100% would indicate pain scores of 10 across the entire time period; 50% would indicate a linear reduction from 10 to 0 over the same time period). In interim and final endpoint analyses, NPRS-%AUC accumulated to date will be compared between groups using an unpaired Student's *t*-test (or nonparametric equivalent). In addition, linear mixed models will be used to compare cumulative pain between SOC and SOC+VR groups over time, as well as pain experienced in the inpatient postsurgical period and following days.

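### The %AUC planning values in 5.6.1 (0.86 versus 0.79) are not on the 0-10 scale defined in 5.6 and reuse the day-2 mean as the SOC day-14 mean, so d = 0.7 and 80% power are not established

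*Combined protocol and SAP*

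**What the plan says.** Section 5.6 defines the secondary endpoint as each patient's percent area under the pain curve over 14 days, built from trapezoids. It fixes the scale with two examples: "100% would indicate pain scores of 10 across the entire time period" and "50% would indicate a linear reduction from 10 to 0 over the same time period". Both place the denominator at a score of 10 for the whole period. The same section says that pain levels are "expected to peak in the first 24-72 hours postoperatively and drop afterward".

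Section 5.6.1 reports preliminary data under standard of care with an "average postoperative pain score of 8.50 following the procedure, and 6.16 on day 2", SD 2.0. For the secondary endpoint it then describes two simulated groups "with day 14 VAS means of 6.16 and 4.93, SD = 2.0", "corresponding to a 7% difference in VAS-%AUC (0.86 versus 0.79; SD = 0.1; difference d = 0.7".

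From d = 0.7 it states: "Data from at least 68 patients is needed to observe a statistically significant VAS-%AUC difference". With 25% attrition this becomes 92 enrolled, 46 per group. Section 5.2.1 plans for about 100: "Approximately 100 Geisinger subjects who have TKA surgery at Geisinger will participate in this study".

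**The concern.** Two features of the planning values do not fit the rest of the plan.

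- **Scale.** On the 5.6 definition, 0.86 means an average score of 8.6 over 14 days. That is above the 8.50 starting mean, although the planning inputs have pain falling to 6.16.
- **Time point.** The SOC day-14 mean of 6.16 is the figure that 5.6.1 has just given for day 2. The SOC+RelieVRx value of 4.93 is 80% of it (0.80 × 6.16 = 4.928), so both arms rest on it.

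The 92 is the largest total sample size stated in 5.6.1 and the one closest to the planned 100. If d = 0.7 does not follow from the endpoint as defined, the 80% power claimed for the only designated secondary endpoint has no stated basis. The primary-endpoint requirements (64 in total; 43 using VR) do not depend on these values.

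**Working it through.** **Inputs from the documents.** Starting mean 8.50; day-14 planning means 6.16 and 4.93; score SD 2.0; %AUC SD 0.1; type I error 5%; power 80%; attrition 25% (all 5.6.1). Denominator 10 and unpaired t-test (5.6). Allocation 1:1 (5.1). About 100 enrolled (5.2.1).

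**Assumptions.** A two-sided test, because sidedness is not stated and this choice reproduces the plan's number. A straight line from start to day 14, because the simulation is not described.

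**1. The plan's own figure.** d = 0.07/0.1 = 0.7. A two-sample t-test needs 34 per group, or 68. Then 34/0.75 = 45.3, rounded up to 46 per group, or 92. Both figures reproduce.

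**2. %AUC on the defined scale.** For a straight line, mean score = (start + end)/2.

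- SOC: (8.50 + 6.16)/2 = 7.33, and 7.33/10 = 0.733
- SOC+RelieVRx: (8.50 + 4.93)/2 = 6.715, and 6.715/10 = 0.672
- Difference: 0.0615, or 6.15 points

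From 8.50, a mean curve that does not rise cannot exceed 0.85. A straight line reaching 0.86 would have to end at 2 × 8.6 − 8.5 = 8.70. An early peak does not explain 0.86, because the preliminary mean is already 6.16 by day 2.

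**3. Origin of the printed values.** 7.33/8.5 = 0.862 and 6.715/8.5 = 0.790, difference 0.072. Dividing by the starting score returns both printed means to two decimals.

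**4. Effect on d.** Dividing means and SD by the same constant leaves d unchanged, so the scale of the SD matters. The text does not state it.

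| If SD 0.1 is on | d | Power, 34 per arm | Power, 37 per arm | Enrolled for 80% |
|---|---|---|---|---|
| 0-10 scale | 0.0615/0.1 = 0.615 | 70% | 74% | 116 |
| 8.5 scale (0.085 on 0-10) | 0.0615/0.085 = 0.72 | 84% | 87% | 84 |

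The 37 per arm is 50 × 0.75 = 37.5, rounded down.

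**5. Sensitivity to what the text leaves open.**

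- *Start-score variation.* With a fixed start and an end-score SD of 2.0, the SD of the line's mean is 2.0/2 = 1.0, which is 0.100 on the 0-10 scale and 0.118 on the 8.5 scale. If the start also varies with SD 2.0 and correlates ρ with day 14, the 0-10 SD is 0.2 × √((1 + ρ)/2). For an assumed ρ of 0 to 0.7 this is 0.141 to 0.184, so d = 0.43 to 0.33 and power at 37 per arm is 45% to 29%.
- *Trajectory, SD held at 0.1.* Take both arms at 8.50 on day 0 and 6.16 on day 2, then 6.16 versus 4.93 on day 14. The %AUCs are (2 × 7.33 + 12 × 6.16)/140 = 0.633 and (2 × 7.33 + 12 × 5.545)/140 = 0.580, so d = 0.53. If the arms already differ from day 2 and then stay flat, they are 0.633 and (2 × 6.715 + 12 × 4.93)/140 = 0.519, so d = 1.14.
- *Lower SOC day-14 mean.* With both arms at 6.16 on day 2, an assumed SOC day-14 mean of 4, 3 or 2 and the test arm 20% lower at day 14, d = 0.34, 0.26 or 0.17.

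**The case against.** The strongest reply is that the scale error has no demonstrated effect on the sample size. A common rescaling leaves d alone, 68 and 92 follow from d = 0.7, about 100 are planned, and the two readings of the SD fall on either side of 80%. This stands as far as it goes. It means the number enrolled has not been shown to be wrong; it does not make the printed means right or supply the missing basis for d.

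A second reply is that 5.6 already provides for checking power at about 25% of the sample and recruiting more if needed. That is a real safeguard, but it does not correct the stated values. If %AUC is part of the check, an observed SOC value near 0.73 would look like a departure from 0.86 when it agrees with the plan's own inputs.

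Three stronger readings are tempting and are not supported:

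- *Means on one scale were divided by an SD on the other.* With a fixed start, 2.0 does give 0.100 on the 0-10 scale. But this needs a two-point line with variation only at the end. The simulation is not described, and 0.118 also rounds to 0.1.
- *The trial is underpowered and needs 116 patients.* That holds in only one of the scenarios above; others need fewer or more.
- *The day-14 value of 6.16 contradicts the preliminary data.* There is no day-14 datum to contradict. It is an unsupported assumption that sits poorly with the expected drop after 24-72 hours.

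Finally, Aim 2 (section 4.2) expects cumulative pain to be comparable between groups. All the power figures here concern detecting a difference, as 5.6.1 does; none addresses showing comparability.

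**Conclusion.** The point holds in a limited form. The printed means and difference are wrong on the plan's own definition: 0.733 versus 0.672 and 6.15 points, not 0.86 versus 0.79 and 7. This rests on the 8.50 start and straight lines to the stated day-14 means, and an 8.5 denominator recovers both printed values. The reuse of the day-2 mean as the SOC day-14 mean is plain on the page; its effect cannot be determined from the documents.

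The size of the consequence is open. With 100 enrolled and 25% attrition, power is about 74% or 87% depending on the scale of the SD, and both figures are illustrations under a straight-line course. Start-score variation and trajectory widen the range in both directions. The supported conclusion is that d = 0.7 and 80% power are not established, not that power is inadequate. The calculation from d to 68 and 92 is correct.

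**What to change.** In section 5.6.1, secondary endpoint:

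- Restate the %AUC means and their difference on the 0-10 definition in 5.6 (0.733 versus 0.672 for the present straight-line inputs).
- Put the SD on that same scale and say how it was obtained.
- Replace the reused day-2 mean with an explicit, justified day-14 assumption for SOC, and derive the SOC+RelieVRx value from it.
- Restate the power and the detectable difference that the planned 100 delivers. Take these from the sponsor's own corrected simulation, not from the illustrations above.
- If %AUC is part of the power check at 25% of the sample, use the restated values there.

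The cost is a rerun of the simulation and a few sentences of text. No change to enrolment, conduct or analysis is requested. The stated 80% power for this endpoint would become conditional on the SD and the day-14 assumption.
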